### **Research Plan**

#### **1. Study Design**

This is a prospective cohort study evaluating safety, cost and patient satisfaction with SDD for patients undergoing minimally invasive sacrocolpopexy for pelvic organ prolapse. A prospectively collected, historical control group who underwent the same surgical procedure will be utilized to compare these outcomes when applicable. SDD will be facilitated in part by a utilizing novel patient education video created for this study and implementing an ERAS pathway. All patients meeting eligibility criteria will be approached for study participation. Outcomes will be assessed on POD 0/1 and at the routine post-operative follow up visit, generally at 6 weeks after surgery.

**Primary outcomes:** The primary outcome of this study is serious adverse events.

#### **Secondary outcomes:**

- Patient-initiated phone calls for a surgery-related complication

- Unscheduled office visits, including voiding trials
- Emergency department visits
- Cost of surgery/post-operative hospitalization
- Quality of Recovery (QoR-15), a validated questionnaire created to measure a patient's early post-operative status
- Visual analog scale (VAS) pain scores
- Minimally invasive sacrocolpopexy survey

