### **Specific Aims**

**Aim 1.** To compare the incidence of adverse events in patients following a SDD protocol for minimally invasive sacrocolpopexy compared to those patients discharged on POD 1.

We hypothesize that there is no difference in the incidence of adverse events between SDD compared to discharge on POD 1 after minimally invasive sacrocolpopexy. Using the *Epic* electronic medical record (**EMR**), we will evaluate 1) the number of unscheduled office visits, patient-initiated calls for a surgery-related complication, emergency department visits, and readmissions/reoperations of patients who had a SDD protocol and 2) the severity of any adverse events using the Clavien Dindo Scale. We will utilize patient phone calls to inquire about any of the aforementioned events outside of our institution. We will compare incidence of postoperative adverse events between patients undergoing SDD versus a historical control group who were discharged on POD 1.

**Aim 2.** To compare the total procedure-related costs associated with SDD compared to discharge on POD 1 for minimally invasive sacrocolpopexy.

We hypothesize that the total costs associated with SDD following minimally invasive sacrocolpopexy is less than the same procedure with discharge on POD 1. We will utilize data from the billing function of *Epic* EMR to compare total procedure-related costs for each approach to minimally invasive sacrocolpopexy.

**Aim 3.** To determine patient satisfaction with SDD after minimally invasive sacrocolpopexy.

We hypothesize that patients will be satisfied with SDD after minimally invasive sacrocolpopexy. We plan to address this aim using a series of validated measures.

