### **3. Data Collection**

The EMR will be reviewed to collect preoperative, intraoperative, and POD 0 data points. We will use the following method to identify the occurrence of a procedure-related adverse event: The EMR will be reviewed for patient phone calls for a procedure-related complication, unscheduled office visits, emergency department visits, hospital readmissions or reoperations within 30 days, and adverse events occurring up to 6 weeks post-operatively. The adverse events of interest will include the following:

- Wound infection
- Hematoma
- Transfusion
- Pelvic abscess
- Osteomyelitis
- Venous thromboembolism (deep vein thrombosis or pulmonary embolism)
- Delayed bowel or urinary tract injury
- Bowel obstruction or ileus
- Cardiac or pulmonary complication
- Neurologic injury

We will also employ an approach that will allow us to capture events that may have been handled outside of the CCHS or in institutions that do not utilize *Epic*. To capture these data points if they exist, we will contact participants by telephone on POD 1 (within 24 hours of surgical completion time) to determine if they received any care from a facility outside of the CCHS and then again at the post-operative follow up visit, which generally occurs at 6 weeks. We will then use these data with the Clavien Dindo Scale to determine the severity of the adverse event, with a grade 3 or higher considered to be a serious adverse event, and we will compare this proportion to the reference proportion of 26.3%. A proportion of patients with grade 3 or higher less than 45.1% will be considered non-inferior to the reference.

As part of the effort to characterize the patient population, we will extract data regarding total procedure-related costs using the EMR. We will assess satisfaction using the quality of recovery questionnaire, visual analog scores for postoperative pain, and a patient satisfaction survey described by Fountain et al at the postoperative visit, which uses a Press Ganey scale for responses (See Appendix A). Please see data collection sheet for a comprehensive list of planned data points.

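### The cost outcome is worded in two ways, with no window or components; followed literally, the listed version leaves out later care and can overstate the saving from same-day discharge

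*Combined protocol and SAP*

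**What the plan says.** Cost appears once in the list of secondary outcomes, as "Cost of surgery/post-operative hospitalization". The other sections use a broader term. Aim 2 under Specific Aims is "To compare the total procedure-related costs associated with SDD compared to discharge on POD 1 for minimally invasive sacrocolpopexy", its hypothesis has a direction ("We hypothesize that the total costs associated with SDD following minimally invasive sacrocolpopexy is less than the same procedure with discharge on POD 1"), and it names the source: "We will utilize data from the billing function of *Epic* EMR to compare total procedure-related costs". Section 3 (Data Collection) repeats the broad term: "we will extract data regarding total procedure-related costs using the EMR". The overall hypothesis at the end of Background & Significance is also about total cost.

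No section says over what period costs are summed, which items enter the sum, or whether care after discharge is costed. Section 3 points to a data collection sheet that is not part of the supplied text.

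Use of later care is specified in more detail. Section 3 has the EMR searched for "unscheduled office visits, emergency department visits, hospital readmissions or reoperations within 30 days", and for adverse events up to 6 weeks. The secondary outcomes list emergency department visits and unscheduled office visits, with voiding trials among the latter, as items separate from cost. Under Day of Surgery, a woman who fails the recovery-room voiding trial returns to the outpatient clinic for a repeat within 2 to 5 days. Participants are also contacted on POD 1 and at the follow-up visit "to determine if they received any care from a facility outside of the CCHS"; no source is given for the cost of such care.

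Section 4 (Statistical Plan) uses 60 historical controls, all discharged on POD 1, for both the adverse-event and the cost comparison.

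**The concern.** Aim 2 asks whether SDD costs less in total. The intervention removes a night that falls inside the listed cost outcome. Costs that early discharge might shift to later care (emergency, clinic and catheter visits) fall outside it on a literal reading. An analyst who follows the outcome list and one who follows Aim 2 would extract different data and could report different savings, and nothing in the plan says which is intended. The choice could also be made after the data are seen.

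At stake is one of the study's three aims. Background & Significance presents the results as necessary for wide adoption of SDD. A lower cost of the index stay, reported as a lower total cost, would not answer the question that Aim 2 poses.

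**Working it through.** The plan states no cost, cost variance or cost sample size, so it has no cost figure to reproduce. Its only sample-size calculation concerns serious adverse events and has no bearing here. The check has two parts.

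**Part 1. Which items each wording covers**

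- Operation and first stay: covered by the listed outcome and by the total-cost wording.
- Emergency department visits: outside the listed outcome read literally; they could be covered by total cost, but no section says so.
- Unscheduled and repeat voiding-trial clinic visits: the same.
- Readmissions and reoperations: unclear under the listed outcome. It does not say index or initial stay, and a readmission is arguably also a hospitalization after the operation. They could be covered by total cost.
- Care outside the health system: not visible in the institution's billing under either wording.

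The two wordings therefore agree on the item that favours SDD and may differ on the items that could offset it.

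**Part 2. How much the difference could matter**

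The unit is the cost of one saved night = 1. Assume first that every SDD woman saves it. Let *c* be the cost of one later event in these units (assumed) and *e* the excess events per SDD woman.

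Share of the saving used up = *e* × *c*. Break-even: *e* = 1/*c*.

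- Clinic visit, *c* = 0.25 (assumed): 1/0.25 = 4 excess visits per woman to cancel the saving.
- Emergency visit, *c* = 1 (assumed): 1 excess visit per woman.
- Readmission, *c* = 5 to 10 (assumed): 1/5 = 0.20 to 1/10 = 0.10 per woman, or 9 to 4.5 in 45 women.
- A heavy mix per 100 women (assumed: 5 more readmissions, 10 more emergency visits at 1 unit, 20 more clinic visits at 0.2 unit): 0.05 × (5 to 10) + 0.10 × 1 + 0.20 × 0.2 = 0.39 to 0.64 of the saving.

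The rates cited in Background & Significance are far lower than those excesses:

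- Minimally invasive myomectomy with SDD: 1.4% readmitted over 3 months. If all of it were excess, 0.014 × (5 to 10) = 0.07 to 0.14 of the saving.
- Vaginal hysterectomy series: 5/1071 = 0.47% readmitted or seen in an emergency room within 30 days. If all of it were excess and costed as readmissions, 0.0047 × (5 to 10) = 0.023 to 0.047.
- Retrospective study of robotic-assisted sacrocolpopexy, 80 SDD against 192 later discharges: no difference found in unplanned visits, emergency visits or readmissions.

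The first two are total rates after other operations, so treating them as excess overstates their effect, but they may not carry over to sacrocolpopexy.

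If only 10 of 12 women save the night, as in the preliminary series at the same institution, the saving per woman is 10/12 = 0.833. The 1.4% rate then uses 0.07/0.833 = 0.084 to 0.14/0.833 = 0.168 of it. The conclusion does not change.

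**The case against.** The strongest reply is that the hypothesis, Aim 2 and the data-extraction instruction in section 3 all speak of total cost, and that one short list entry should not override them. No section excludes later care from cost, and the data collection sheet, which was not supplied, may list the components. This stands against one tempting inference, that later care will never be costed: the documents do not support it. It does not remove the inconsistency. The list entry is the only place where cost is named as an outcome, it is narrower than the aim, and no supplied text settles the window.

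A reader might also infer that SDD must look cheaper by construction. That is too strong as well. Women who miss the discharge criteria stay overnight, and their cost counts if they are analysed in the SDD cohort. The controls come from a trial that finished recruiting in 2017, so other cost differences between the cohorts can move the result either way. Saving a night pushes the comparison in one direction without fixing its answer. The reassurance from overnight stays is itself partial, because the exclusion criteria remove women whose complications require admission.

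A third reply is that a large bias needs event excesses well above anything the documents cite. That stands, and it limits the size of the point.

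Finally, one might wish to impute a cost for outside care. Telephone and visit capture is described for study participants only, with no equivalent for the historical controls, so imputation could add cost to the SDD cohort alone. With about 45 women there may also be no in-system event of the same type from which to take a mean.

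**Conclusion.** The cost outcome is inconsistent with Aim 2 and has no stated window or components. If the listed version is followed literally, the saving is overstated by the cost of any extra emergency, unscheduled and voiding-trial visits under SDD, and possibly of extra readmissions and reoperations. If later care is equal in the two cohorts, there is no such bias.

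The size cannot be computed from the documents. With an assumed readmission cost of 5 to 10 saved nights, the cited readmission rates would use at most 0.07 to 0.14 of the saving (0.084 to 0.168 if only 10 of 12 women save the night). Cancelling it would take 10 to 20 excess readmissions per 100 women. A reader might conclude that the omission could reverse the cost result; the cited rates point to a smaller saving instead. They come mostly from other operations, and the sacrocolpopexy comparison, with 80 SDD women, does not exclude a modest excess. Clinic visits alone would shrink the saving rather than reverse it.

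This concerns a secondary outcome. It is still worth correcting before the billing data are extracted, because the outcome as listed does not answer the aim and the correction is cheap.

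**What to change.** Replace the cost entry under Secondary outcomes with one definition, and use it in Aim 2 and section 3: total procedure-related cost from the day of surgery to 6 weeks, taken from Epic billing. It should include the operation and index stay, unscheduled and voiding-trial visits, emergency department visits, readmissions and reoperations, with the same window and components in both cohorts. Base the Aim 2 conclusion on this total, and show the index-stay cost as a component.

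Keep the main comparison to in-system billed care in both cohorts. Report outside-system care learned from participants as counts, and name its missing cost as a limitation. Impute that cost only if the same capture exists for the historical controls.

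The change needs revised wording and a longer date range in the same billing extract for both cohorts, on the assumption that the controls' billing records reach 6 weeks. It needs no new patients or visits. The price is somewhat more variance in cost and possibly a smaller apparent saving.

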## **Paradigm**

### Preoperative Visit

Participants will be prospectively identified by the primary surgeon when the decision is made to proceed with a minimally invasive sacrocolpopexy. A chart review by the primary investigator will be performed to ensure eligibility criteria is met, after which all patients will be called explaining the purpose of the study, risks, benefits and alternatives to participation. A telephone encounter in the EMR will document this informed consent process. Documentation including signing the consent form will be obtained at the preoperative visit or on the day of surgery.

Thorough preoperative surgical counseling will then take place at the preoperative visit as per our standard protocol. A patient education video, approximately 10.5 minutes in length, developed by the primary investigator will be administered to all patients either during preoperative visit or prior to her scheduled surgery and will address:

- The expectation that eligible patients will be discharged home the same day following surgery
- Normal postoperative symptoms and care
- Warning signs (e.g. pain, vaginal bleeding, nausea/vomiting, fever, urinary retention) and restrictions
- The possibility of being discharged home with an indwelling catheter if unable to void after surgery
- The importance of the presence of a caregiver postoperatively

Contact information and instructions for postoperative questions/concerns will be given to the patient.

Prescriptions will also be provided for analgesia, a bowel regimen, and postoperative nausea and vomiting prophylaxis, so that all medications will be immediately available upon discharge after surgery.

### Day of Surgery

**An ERAS protocol for preemptive analgesia, postoperative nausea and vomiting, fluid balance, and postoperative oral intake will be used on the day of surgery to help facilitate SDD.**

*Fasting:* Patients will be instructed to take no food by mouth starting at midnight the day of surgery. Clear liquids will be allowed up to 3 hours before surgery. This protocol is in accordance with Cleveland Clinic Anesthesia protocols.

*Preemptive Analgesia:* Prophylactic medications (if no contraindications) will be given upon arrival to the hospital on the day of surgery for increased postoperative pain relief, decreased narcotic consumption, and patient satisfaction. These orders will be placed as part of the pre-operative order set and will include: celecoxib 400 mg PO, acetaminophen 1,000 mg PO and gabapentin 600 mg PO. For patients 65 years old or <50 kg, a reduced, 200mg dose of gabapentin will be provided. One dose of ketorolac (30 mg IV or 15 mg IV in patients 65 years old or <50 kg) will be given at incision closure if no contraindications exist. Use of intradermal analgesia will be at the discretion of the primary surgeon. Sparing use of IV opioids intra-operatively and in the post anesthesia care unit (PACU) will be at the discretion of anesthesiology.

*Postoperative Nausea and Vomiting:* Prescription for scopolamine transdermal patch and instructions for use will be provided at the preoperative visit for any patients with a history of postoperative nausea and vomiting if no contraindications exist (e.g. angle closure glaucoma).

- Dexamethasone 4mg IV once prior to incision ( $\pm$  30 min) if no contraindications exist.
- Ondansetron 4 mg IV once prior to incision closure ( $\pm$  30 min) if no contraindications exist.
- Antiemetic medications may be given in the PACU at the discretion of anesthesiology.

*Fluid balance:* The goal will be to maintain intraoperative euvolemia. After surgery, the peripheral IV will be saline locked when tolerating PO intake in the PACU.

*Postoperative Oral Intake:* Early feeding will be encouraged, and a regular diet may be resumed immediately following surgery. Amount and type of food consumed may be determined by the patient.

*Vaginal Packing:* Avoidance of vaginal packing will be encouraged, however, if packing is placed, it will be removed in the PACU by a staff, fellow, or resident prior to the voiding trial.

*Voiding Trial:* Our standard voiding protocol will be performed in the PACU when the patient is able to stand and ambulate to the restroom. The bladder will be retrograde filled with 300 ml of sterile fluid. The Foley catheter is then removed and the patient must void 200 ml (or 2/3 of the instilled volume if the patient is not able to tolerate the full amount). If the patient is unable to void then the Foley catheter will be replaced and she will be given Foley teaching or, alternatively, the patient may be taught intermittent self-catheterization. A repeat voiding trial will be scheduled within 2-5 days in the outpatient clinic.

*Post-operative Assessment and Disposition:* All patients will be assessed by the primary surgical team prior to discharge home. Post-operative requirements include: Ability to tolerate oral fluids and medications, adequate pain control and ability to walk with assistance. Patients not meeting criteria for discharge home at the conclusion of the recovery period will be kept for observation overnight as an extended recovery.

#### Post-operative Follow-up

- POD 0: All patients will be contacted by an individual on their surgical team to see how the patient is doing. If patients have a late discharge from the hospital, after 1700, a POD0 call will not be initiated. This call will last approximately 5 minutes in length (or as dictated by patient questions or concerns), to occur between 1500 and 1900 on day of surgery.
- POD 1: All patients will be contacted within 24 hours of their surgical completion time by a registered nurse or a physician. This call will last approximately 10 minutes in length.
- All patients will have a scheduled post-operative visit at ~6 weeks, as per our standard protocol.

## **2. Study Population and Subject Identification**

### **Eligibility Criteria**

Patients of the Center of Urogynecology and Pelvic Reconstructive Surgery in the Department of Ob/Gyn and Women's Health Institute or the Female Urology division in the Department of Urology at the Cleveland Clinic scheduled to undergo a minimally invasive (robotic-assisted or laparoscopic) sacrocolpopexy for pelvic organ prolapse with a board-certified female pelvic medicine and reconstructive surgery specialist will be approached for participation in this study.

Additional surgical procedures may include: hysterectomy (either total or supracervical), trachelectomy, anterior and/or posterior colporrhaphy, enterocele repair, minimally invasive Burch colposuspension or paravaginal defect repair, vaginal mesh removal or revision, vaginal graft placement, midurethral sling, or perineal rectal prolapse repair (Delorme or Altemeier).

### Inclusion Criteria:

Preoperative requirements include:

- Age <80 years old
- Preoperative American Society of Anesthesiologists grade I (normal healthy patient) or II (mild systemic disease)
- Access to ancillary care, including phone advice, nurse and outpatient clinic numbers
- Caretaker at home for at least 24 hours post-operatively
- Able to speak and read English
- Has decision-making capacity and able to provide consent for research participation

### Exclusion Criteria:

- Laparoscopic, robotic, or open abdominal surgical procedures that require an overnight admission. This may be due to unanticipated additional intraoperative procedures or surgical complications such as unintentional cystotomy or enterotomy, hemorrhage, or anesthetic complication.
- Patients undergoing concomitant laparoscopic colorectal procedures or anal sphincteroplasty
- Surgery start time after 1:00PM, as previous studies have determined this is associated with a decreased likelihood of SDD
- Pregnancy or positive hCG testing, which is standard of care preoperative testing.

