ERAS pathways can have an important role in other areas of gynecologic surgery. In the field of urogynecology, quality of life reconstructive surgery is often performed to address symptoms of pelvic organ prolapse, urinary incontinence, and/or fecal incontinence. A prospective study by Kalogera et al evaluated the impact of an ERAS pathway for patients undergoing vaginal reconstructive surgeries for pelvic organ prolapse versus historical controls. In this cohort, patient satisfaction with perioperative care was high, mean duration of hospital stay was significantly reduced, and there were no differences in 30 day outcomes. In a case series by Zakaria and Levy, an ERAS pathway was utilized after vaginal hysterectomy, which permitted SDD in 96% of patients. Notably, only 5 of the 1071 patients required readmission or emergency room evaluation within 30 days of surgery. Taken together, these studies provide support for the application of ERAS pathways in urogynecology, where well-selected surgical candidates are undergoing surgeries appropriate for SDD.

Yet, to date, **only one research study has investigated the role of SDD after minimally invasive sacrocolpopexy**. A sacrocolpopexy is a surgery for pelvic organ prolapse in which a bridging piece of mesh is utilized to suspend the vaginal cuff to the anterior longitudinal ligament overlying the sacral promontory. This is an extensively studied and highly effective surgical technique to correct pelvic organ prolapse and is a mainstay in the field of urogynecology. A study by Faucheron et al evaluated SDD for robotic and laparoscopic ventral rectopexy, a similar mesh-augmented procedure that is performed for rectal prolapse, and concluded that SDD is feasible and safe. A preliminary study by Lloyd et al performed at the Cleveland Clinic within the Female Urology division investigated SDD after minimally invasive sacrocolpopexy (*article in press*). In this study, SDD was achieved in 10 of 12 patients (83.3%). The two patients who did not have SDD were due to case completion after 6PM, a preset case completion requirement. Outcomes were also retrospectively compared between patients who underwent SDD (N= 10) and patients who stayed overnight (N=30). Only one

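### Consented women are excluded for intraoperative complications that require overnight admission, a rule that cannot be applied literally to the POD 1 controls, and the primary analysis set is not named

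*Combined protocol and SAP*

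**What the plan says.** The Study Design section states: "The primary outcome of this study is serious adverse events". Data Collection defines a serious event as Clavien Dindo grade 3 or higher, compares the proportion with 26.3%, and declares non-inferiority if it is below 45.1%.

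On the timing of enrolment, the Preoperative Visit section says: "Documentation including signing the consent form will be obtained at the preoperative visit or on the day of surgery". The first item under Exclusion Criteria then removes procedures that require overnight admission, and adds: "This may be due to unanticipated additional intraoperative procedures or surgical complications such as unintentional cystotomy or enterotomy, hemorrhage, or anesthetic complication". Those reasons can only become known once the operation is under way.

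A separate rule under Day of Surgery covers women who do not meet the discharge requirements after recovery. They "will be kept for observation overnight as an extended recovery". Nothing says expressly whether they count in the primary proportion.

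Aim 1 describes the study group in two ways: "patients following a SDD protocol for minimally invasive sacrocolpopexy compared to those patients discharged on POD 1", and later "patients undergoing SDD versus a historical control group who were discharged on POD 1". The Statistical Plan describes the 60 controls, drawn from an earlier randomized mesh trial, as matching the eligibility criteria and as all having gone home on POD 1. Neither Data Collection nor the Statistical Plan defines an analysis set.

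**The concern.** A safety proportion is being calculated after some enrolled women have been removed for the way their operation went. If those women later have more grade 3 events than average, the reported SDD rate is too low for anyone who wants to know what happens to all women who start surgery on this pathway.

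The control comparison has a related problem. Every control stayed overnight, so requiring an overnight admission cannot distinguish a complicated control from an uncomplicated one. If a woman with a cystotomy is removed from the SDD cohort while a similar woman stays among the controls, part of any Aim 1 difference reflects selection. The planned logistic regression cannot restore women who have been removed.

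With no analysis set named, the choice could also be made after the results are known. What is at stake is the meaning of the reported rate and the fairness of the control comparison.

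**Working it through.** **The plan's own figure.** An exact one-sided binomial test of 26.3% with n = 45 and alpha 0.05 rejects at 18 or more events (actual alpha 0.031). Its power at 45.1% is 0.798, so the stated 80% reproduces. Allowing for 3% dropout, 45/0.97 = 46.4, which rounds up to 47. The point below does not depend on this calculation.

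**Order of events.** Consent comes at the preoperative visit or on the day of surgery; the intraoperative course follows; exclusion follows that; grade 3 events are counted to 6 weeks. The exclusion is therefore made after enrolment and on the basis of the surgical course.

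**Effect on the reported rate.** Let t be the rate in all who start surgery, f the share excluded and q the event risk of those excluded. Then

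reported rate = (t − f·q)/(1 − f).

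The protocol considers t = 12% representative. It gives no intraoperative complication rate, so f = 2-5% (47 × 0.02 = 0.9 to 47 × 0.05 = 2.4 women) and q = 0-50% are assumptions.

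| q | f = 2% | f = 5% |
|---|---|---|
| 0% | 12.2% | 12.6% |
| 12% | 12.0% | 12.0% |
| 25% | 11.7% | 11.3% |
| 50% | 11.2% | 10.0% |

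Example: (0.12 − 0.05 × 0.5)/0.95 = 0.095/0.95 = 10.0%. The error runs from 0.6 points too high to 2.0 points too low, so its sign depends on q. With t = 26.3% and f = 5%, the reported rate is 27.7% at q = 0 and 25.1% at q = 50%.

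**As counts.** 6/47 = 12.8% among all starters becomes 5/45 = 11.1% if two women are excluded and one of them had an event.

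**Against sampling error.** The exact 95% confidence interval for 5/45 is 3.7% to 24.1%. For 45 against 60 women at 12%, the standard error of the difference is √(0.12 × 0.88 × (1/45 + 1/60)) = 0.064. A 2-point gap is 2.0/6.4 = 0.31 standard errors.

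**Against the decision rule.** At most 20/45 (44.4%) or 21/47 (44.7%) is below 45.1%. The probability of passing at a true 26.3% is 99.7% (n = 45) or 99.8% (n = 47), and above 99.99% at 12%.

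**Which women are in the cohort.** The formal statement of Aim 1 uses pathway wording. The Day of Surgery section calls an overnight stay after missed discharge requirements an extended recovery, whereas the exclusion concerns procedures requiring admission. The Appendix A survey offers discharge one day, and two or more days, after surgery. Together these favour keeping extended-recovery women in the cohort, but no sentence says so, and the second Aim 1 wording points to actual discharge.

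**The case against.** The strongest reply is that the exclusion is a disclosed choice of target. Aim 1 is about postoperative events after a discharge strategy, and the listed complications occur before any discharge decision. Limiting the cohort to women who could still go home the same day is legitimate. This stands. What remains is that the plan does not state that target or show that it was applied equally to both cohorts.

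A reader might infer that the rule deletes primary events. The documents do not support this. The event list in Data Collection names only delayed bowel or urinary tract injury, so a cystotomy or enterotomy found during surgery need not be a counted event. Transfusion is on the list, but the Sample size paragraph describes grade 3 as needing surgical, endoscopic or radiologic imaging/intervention, which transfusion alone does not meet. A low-biased rate requires the excluded women to have higher later risk, and the documents do not show that.

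A reader might also infer from the in-house pilot that women kept overnight drop out of the denominator. It had 12 women on the plan, 10 of whom went home the same day, and its outcome comparison used those 10. But it is a separate study. Both of its overnight stays followed case completion after 6 PM, and this protocol excludes starts after 1:00 PM, so its 83.3% may not carry over.

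On the controls, the protocol does say that they match the eligibility criteria, and the named complications could be checked in their records. A cohort all discharged on POD 1 also contains nobody kept longer, so it too is filtered by its course. These points stand, but they do not show that the filters are the same.

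**Conclusion.** The concern holds as a minor design point. The grade 3 or higher proportion describes women selected after surgery starts, the exclusion cannot be applied as written to controls who all stayed overnight, and the primary analysis set is not named. Confidence in that textual gap is high; confidence in the size of any bias is low.

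Under the assumed 2-5% exclusion and 0-50% event risk, a true 12% shifts by between +0.6 and −2.0 points, at most about 0.3 standard errors of the control comparison. A reader might go further and conclude that the safety rate is shown to be understated or that the non-inferiority verdict is undermined. Neither follows: the direction depends on a risk that the documents do not give, and the 45.1% rule is passed with near certainty at either 12% or 26.3%. The primary test is against a fixed reference, so the control problem bears on the Aim 1 cohort comparison. The 26.3% reference is not described as carrying a similar exclusion.

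**What to change.** Follow all consented, preoperatively eligible women who start surgery by 1:00 PM to 6 weeks. Report the grade 3 or higher proportion, against 26.3% and against the controls, in two sets:

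1. all of these women, whatever the intraoperative course or discharge day;
2. the set left after the intraoperative exclusion.

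Name in advance which is primary. For set 2, check the 60 control records against the same intraoperative-complication list, rather than against overnight admission. Report the number, reasons and outcomes of women excluded after surgery starts, and caution that the 26.3% reference is not described as having this exclusion. State that extended-recovery women remain in both sets, and reconcile Aim 1, the disposition rule under Day of Surgery and the Exclusion Criteria accordingly.

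The cost is analysis-set wording, a review of 60 control records, and record follow-up of an estimated one or two already consented women under the 2-5% assumption. The downside is that the all-starters set describes the planned-SDD pathway rather than only women still suitable for SDD, and may show a slightly higher event rate.
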